3.2 Objectives

The main trial includes an internal pilot to determine the feasibility of site set-up and participant recruitment, the waiting times for the intervention group to receive resection and the number of control participants who undergo resection.

Internal pilot objectives:

- A. To assess the feasibility of conducting two multi-centre RCTs of hysteroscopic resection of submucous fibroids and endometrial polyps in women suffering from infertility or recurrent miscarriage, by conducting two RCT internal pilots; one for women with endometrial polyps and one for women with submucous fibroids.

Main trial objectives:

The objectives of the main trial are:

- A. To determine the clinical and cost-effectiveness of the hysteroscopic removal of endometrial polyps compared to no hysteroscopic removal to improve fertility in women suffering from infertility or recurrent miscarriage.
- B. To determine the clinical and cost-effectiveness of the hysteroscopic removal of submucous fibroids compared to no hysteroscopic removal to improve fertility in women suffering from infertility or recurrent miscarriage.
- C. To determine patient experience and satisfaction, and procedure related complications.
- D. To assess the long-term effect of hysteroscopic resection of endometrial polyps and submucous fibroids, by collecting and analysing routinely collected NHS data.

The outcomes used to assess these objectives are described in section 8.

4. Trial Design

The following study will be conducted in accordance with the protocol and ICH GCP.

The trial is designed as an “Umbrella” RCT (31) with two concurrent pragmatic, parallel group, open, multi centre RCTs. Methods for each RCT will be the same except where described here separately. A trial summary flow diagram is provided in Figure 2.

RCT1: Submucous fibroid population: women with a history of infertility or recurrent miscarriage and trying to conceive naturally or with fertility treatment and who meet the inclusion criteria will be randomised (1:1) into hysteroscopic resection vs no hysteroscopic resection of the submucous fibroid.

RCT2: Endometrial polyp population: women with a history of infertility or recurrent miscarriage and trying to conceive naturally or with fertility treatment and who meet the inclusion criteria will be randomised (1:1) into hysteroscopic resection vs no hysteroscopic resection of the endometrial polyp.

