10.2 Recording and reporting

AEs and SAEs are defined as an event that occurs after the patient has provided written informed consent for trial entry and up to completion of the 24 month follow-up by the last participant recruited (LPLV).

Hysteroscopic resection of submucous fibroids and endometrial polyps is a routine procedure for which the side effects are understood. Therefore, only those AEs which are deemed serious or of particular relevance to the procedure will be recorded / reported in this trial. These are listed as 'expected AEs' in Table 4.

Adverse Events

Participants will be asked for any details of adverse events, at four time points up to the participants' final study related follow-up event; post procedure (if randomised to receive hysteroscopic resection of submucous fibroids or endometrial polyps), then at 6, 15 and 24 months post randomisation. AEs or SAEs may also be identified by the Research Nurse/Associate PI/Dr, or any other individual, at any point during the study, up to last patient last visit.

When an event is identified the process for recording and reporting outlined in Figure 5 will be followed. The local PI (or other suitably trained member of research staff, if the task is delegated to them) should be notified immediately and assess the event for classification as an SAE (see definition in section 10.1).

AEs confirmed as NOT serious will be checked against the list of expected AEs (Table 4).

Expected AEs

AEs which are expected will be recorded by site staff in the participant CRF.

Unexpected AEs

AEs which are not expected will not be recorded on the basis that hysteroscopic resection of submucous fibroids and endometrial polyps is a routine procedure, for which the side effects are understood. We do not anticipate any AEs, which are of relevance to the intervention, other than those listed in Table 4, unless the site PI considers the events to be significant.

Sites are asked to enter all available information onto the study database as soon as possible after the site becomes aware of the event.

Table 4 - Expected Adverse Events

Gynaecological / obstetric related	Procedure related (immediate)	Procedure related (delayed)

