11.2 Statistical Analysis

Data from the two trials will be analysed and reported separately. Both trials have the same primary and secondary outcomes so the analysis and reporting will be similar. As both trials are pragmatic parallel group RCTs, data will be reported and presented according to the latest CONSORT guidelines. The statistical analyses will be performed on an intention-to-treat basis. Under the strict intention to treat (ITT) principle, all women will be included in the analysis once they are randomised as per the allocated treatment regardless of what happens after randomisation. All statistical exploratory tests will be two-tailed with alpha = 0.05.

Interim Analysis

There is no formal planned interim analysis other than the assessment of recruitment, treatment uptake and withdrawal from randomised treatment allocation after the 9-month internal pilot phase, and the assessments of clinical pregnancy and live birth rates in the control arm after 50% of randomised participants have been randomised and followed up for 15 months, respectively.

At the first interim assessment, the clinical pregnancy rate will be calculated in the control arm. If lower than the 10% estimate used for LBR in the control arm in the sample size estimation, sample size re-estimation will be considered, under the guidance of the DMEC. If greater than or equal to 10%, no adaptation will be made and the next interim assessment will take place when 50% of participants have completed the 15-month follow-up.

At the second interim assessment we shall calculate the LBR and its associated 95% CI for participants in the control arm. If the CI includes the 10% LBR (which we assumed for the control group in the sample size calculation) then we will continue to recruit to the original target sample size.

If the CI for the LBR in the control arm does not include 10% then we will re-estimate the sample size using the point estimate for the LBR we have observed thus far in the control arm and the same target difference of 10%. If this results in a reduction in the target sample size we will continue to recruit to the original target sample size (of N=560). If this results in an increase in the target sample size we will seek the opinion of the independent DMEC and TSC about increasing the sample size.

Baseline assessments

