- ii. a GLM either with a Binomial or Poisson distribution and identity link function (41).

In either case, a GLM with a Binomial distribution will be the first choice. In the case of a GLM with a Poisson distribution, robust adjusted standard errors will be used (39–41).

Any noted differences between the unadjusted and adjusted primary analyses will be highlighted.

Missing primary outcome data

A default conservative ‘worst case’ scenario will be adopted as the primary approach for all the analyses, unless stated otherwise. Here, a woman whose live-birth outcome is unknown for some reason(s) contribute to a negative outcome, that is, they shall be assumed to have failed to produce a live birth. Due to multiple pregnancy, there is a possibility that some pregnant women may achieve multiple births resulting in potential multiple live births outcomes from a single mother. The default approach for dealing with multiple births for the primary analysis will be that a live birth is counted as a single event regardless of how many babies are born during that live birth.

A sensitivity analysis for the primary outcome, LBR, with missing birth outcome data, will be imputed through a “best” case (i.e. assume the woman had a successful live birth) and multiple imputation with chained equations and the results compared with the default analysis.

Non-compliance and contamination

Further sensitivity analysis for the primary outcome, LBR, will be undertaken to adjust for non-compliance and contamination (i.e. use of treatment by individuals in the control arm) using methods described in Cuzick et al (42) and the results compared with the default ITT analysis.

Analysis of secondary outcomes

Secondary binary outcomes such as the LBR at 24 months, multiple birth rate, implantation rate, clinical pregnancy rate, miscarriage rate, ectopic pregnancy rate, pre-term delivery rate and still

birth rate will be analysed in a similar way to the primary outcome. The denominator for the calculation of the rates will be number of participants randomised to the intervention and control arms respectively. We shall also repeat the above analyses on the per protocol population.

The ITT population (and safety) populations will consist of all women who consent and are randomised to receive or not receive hysteroscopic removal of submucous fibroids or endometrial polyps.

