The per protocol population for those randomised to receive hysteroscopic removal of submucous fibroids or endometrial polyps is defined as a patient a) attending the clinic for the hysteroscopic excision of submucous fibroids and or endometrial polyps and b) receiving the procedure per protocol (following the sites usual procedures for hysteroscopic removal of submucous fibroids and / or endometrial polyps) within the first six-months post-randomisation. The PP population for those randomised to the control group and not to receive hysteroscopic removal of submucous fibroids or endometrial polyps is defined as a patient a) attending the clinic and b) not undergoing hysteroscopic removal of submucous fibroids or endometrial polyps procedure per protocol within the first six months post-randomisation.

Safety and adverse events

Adverse events including serious adverse events (death; hospitalization (initial or prolonged); disability or permanent damage; other important medical events), will be reported for each randomised group and compared between the two groups using a Fisher's Exact test or Chi-squared test (as appropriate). A 95% confidence interval (CI) for the difference in adverse event rate between the groups will also be calculated.

Sub-group analyses

An exploratory sub-group analysis using multiple logistic regression, with the primary outcome LBR, will look for an interaction between treatment group and the following sub-groups: a) infertility/recurrent miscarriage and b) type of fertility treatment received. A sub-group analysis looking at interaction between treatment group and type of submucous fibroid may be carried out if a sufficient number of control participants undergo diagnostic hysteroscopy, as part of site's usual diagnostic procedures, with fibroid type identified.

Analysis of time to event outcomes

Within the main trial period all women recruited to the trial will be followed up for a minimum of 2 years post-randomisation. Given the study recruitment will take 2.5 years then the first recruited women will have up to 4.5 years follow-up. Women will be censored at the last known date of follow-up if they have not had a live birth/clinical pregnancy.

Intervention waiting times and withdrawal from randomised treatment

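### Safety is specified by randomised group, which does not give the complication risk per woman resected, although procedure-related complications are a main objective

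*Protocol*

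**What the plan says.** **Objective.** Main trial objective C in Section 3.2 reads "To determine patient experience and satisfaction, and procedure related complications". Section 8.3 carries it forward as safety outcome 13.

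**Analysis.** Section 11.2 sets strict intention to treat: "all women will be included in the analysis once they are randomised as per the allocated treatment regardless of what happens after randomisation". It then gives safety the same population: "The ITT population (and safety) populations will consist of all women who consent and are randomised". Its safety paragraph says that adverse events, serious ones included, "will be reported for each randomised group and compared between the two groups", by Fisher's exact or chi-squared test, with a 95% CI for the difference. No safety set by treatment received is defined.

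**Other analyses.** The sentence "We shall also repeat the above analyses on the per protocol population" follows the secondary pregnancy and birth outcomes and comes before the safety paragraph. The adjustment for non-compliance and contamination is stated for the live birth rate. The treatment-switching methods are introduced for time to live birth.

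**Events and collection.** Table 4 (Section 10.2) separates obstetric events from immediate and delayed procedure-related events. The first enquiry about adverse events is "post procedure (if randomised to receive hysteroscopic resection of submucous fibroids or endometrial polyps"), followed by 6, 15 and 24 months. Section 9.1 has the operator record complications during the procedure, for women allocated to the intervention arm only.

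**The concern.** Several procedure-related entries in Table 4, such as return to theatre, presuppose an operation. With all randomised women as the denominator, a woman allocated to resection who never has it counts as a resection without complications. A control woman injured at a later resection counts as an event under no resection. Both pull the two arms together.

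The protocol foresees both departures. Intervention women may decline surgery, be withdrawn from it for clinical reasons, or conceive first and stay in the trial (Sections 6.1 and 9.2). Control women may choose resection. For the live birth rate, Section 11.2 itself recognises that an analysis by allocation then estimates only the effect of a policy, and it adds further analyses for efficacy. It adds none for safety.

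At stake is the figure that readers will take as the complication risk of resection. Section 2.1 makes surgical risk part of the case for the trial.

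**Working it through.** **The protocol's own figure.** It states no complication rate. Its sample size supplies the arm size, so that was checked first. With 10% v 20%, 5% two-sided, 90% power and mean proportion 0.15:

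- n = [1.960 × √(2 × 0.15 × 0.85) + 1.282 × √(0.10 × 0.90 + 0.20 × 0.80)]² / 0.10² = 265.9, so 266 per group and 532 in total.
- 532 / 0.95 = 560 randomised, or 280 per arm at 1:1. This agrees with Section 11.1.

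**Formula.** Let r be the complication risk per woman resected, u the final proportion of the intervention arm resected, and c the final proportion of the control arm resected. For events that only resection can cause, and with the same r in both arms:

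- intervention arm shows r × u
- control arm shows r × c
- difference = r × (u − c)
- women resected, both arms pooled: 280r(u + c) events / 280(u + c) women = r, whatever u and c are.

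**Illustrations.** The documents give no value for r, u or c; all the values below are assumptions. Here r = 5%, with 280 per arm.

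| u | c | Intervention | Control | Difference | As a share of r |
|---|---|---|---|---|---|
| 100% | 0% | 5.0% (14.0 women) | 0% (0) | 5.0 points | 1.00 |
| 90% | 5% | 4.5% (12.6) | 0.25% (0.7) | 4.25 points | 0.85 |
| 80% | 10% | 4.0% (11.2) | 0.5% (1.4) | 3.5 points | 0.70 |

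In the last row 280 × (0.80 + 0.10) = 252 women are resected and 11.2 + 1.4 = 12.6 have events. 12.6 / 252 = 5.0%, so the per-woman-resected table recovers r.

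For other values of r at u = 80% and c = 10%, the difference is 0.7 points (r = 1%), 2.1 points (r = 3%) and 7.0 points (r = 10%).

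**Does another planned analysis cover it?** The per-protocol repeat does not name adverse events. If it were extended to them, it would drop control women resected within six months instead of counting their complications under resection, and it would leave later resections in the control group. The contamination adjustment names only the live birth rate.

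**Collection.** Section 8.3 (outcome 11) counts control women who are resected, so their number is available as a denominator. Their operative detail is not: Sections 8.3 and 9.1 limit it to the intervention arm, and Section 1.5 shows that version 2.0 removed it for control women deliberately.

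**The case against.** - **Analysis by allocation is a sound choice.** It is unbiased for the policy of offering resection, which is the natural question in a pragmatic trial. For the obstetric events in Table 4, a comparison by treatment received would be confounded. This stands, and the randomised comparison should stay.
- **Intervention-arm data already exist.** The operator's form, the post-procedure enquiry and the compliance record (Section 6.1) allow complications per woman resected to be tabulated in that arm. This stands. It makes the fix cheap, but the protocol does not specify the table.
- **An extra table belongs in the statistical analysis plan.** That plan may indeed add one, and the protocol does not rule it out. However, the protocol does more than stay silent: it fixes the safety population and the grouping, and neither yields the quantity in objective C.
- **The pilot criteria do not give the size.** A reader might take 80% uptake and 10% to 50% crossover from Table 1 and conclude that harm will be understated by 30% to 70%. The documents do not support that. Those are pilot thresholds at 3 and 6 months, not final values. Section 6.1 aims at an 18-week pathway, about 4.1 months (18 × 7 / 30.4), so women treated to schedule can miss the 3-month mark and still be resected. Section 8.2 expects control women seldom to be resected within 6 months.
- **Crossover events are not simply lost.** A reader might also infer that complications of control-arm resections go unrecorded. Section 10.2 lets staff identify events at any time up to the last patient's last visit, and serious events in either arm are reported within 24 hours or one working day (Sections 10.2 and 10.4). The remaining gap is prompt enquiry about non-serious events.

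**Conclusion.** The point holds as a minor one. For procedure-only events, the specified analysis does not give the risk per woman resected. The arms show ru and rc and differ by r(u − c), so any departure from allocation lowers the difference below r.

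The size is unknown because the protocol forecasts neither u nor c. It is nil with full adherence; 0.7r is only an illustration. This is a mismatch between objective C and the stated denominator, not a bias in the randomised comparison, which remains valid for its own question.

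The algebra assumes one risk r in both arms, complete ascertainment, and no such events without resection. The last may not hold exactly: control women randomised during hysteroscopy have had that procedure, and infection can have other causes. With a background risk b in unresected women the difference becomes (r − b)(u − c), which leaves the conclusion unchanged.

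The collection point is secondary. Because the post-procedure enquiry follows allocation, non-serious complications of control-arm resections may be under-ascertained.

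**What to change.** 1. Keep the comparison by randomised group for all adverse events.
2. Add to Section 11.2 a descriptive table of the procedure-related events in Table 4, with women actually resected as denominator, whichever arm they were allocated to. Label it as non-randomised and show the allocated arm alongside, because ascertainment differs between arms.
3. In Section 10.2, tie the post-procedure adverse event enquiry to undergoing resection instead of to allocation. Failing that, state that non-serious events in control women who are resected may be under-ascertained.

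**Cost.** Item 2 is one extra table, with no effect on sample size or the primary analysis. Item 3 is a small amendment to adverse event collection, but it needs HRA and ethics approval and must reach about 30 sites. It also partly revisits the version 2.0 decision to collect less from control women who are resected. If that is judged disproportionate, the statement of limitation costs one sentence.

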6.1 Patients randomised to Intervention Group

Hysteroscopic resection of submucous fibroids and endometrial polyps is currently undertaken routinely in the NHS for women suffering from miscarriage or infertility.

In order for this study to be applicable to the wider NHS, a pragmatic approach will be taken, and hence we will accommodate local hysteroscopic procedures conducted at the participating centres using existing surgical techniques and setups. Techniques will include the use of bipolar or monopolar resectoscopes, hysteroscopic morcellators or scissors or polyp snares. The procedure may be performed in an outpatient or inpatient setting. For large abnormalities, further surgical procedures may be required. Type 0 and Type I submucous fibroids are more easily resectable than Type II. Clinical / operator judgement will be used to determine the intra-cavitary portion that is resectable for Type II fibroids. As per usual practice, women randomised to receive the intervention will be asked to use contraception prior to hysteroscopy taking place, if applicable. A pregnancy test may also be undertaken. This is in line with routine clinical care and the World Health Organisation (WHO) checklist prior to resection (33). In the event that a patient allocated to intervention has a positive pregnancy test before receiving hysteroscopic resection, the patient will remain in the trial and followed-up as per the schedule in 9.1.

Scheduling treatment

For participants allocated to the intervention group, sites should aim to schedule the appointment for hysteroscopic resection within the 18-week patient pathway. However, with the current COVID-19 pandemic the procedure should be scheduled within the site's own current guidelines. Participants expecting to receive other fertility treatments e.g. IVF, ovulation induction, IUI, Donor Sperm Insemination, ICSI or medications e.g. clomid, should commence with this treatment as soon as possible following hysteroscopic resection. This does not include any research infertility interventions as these are exclusion criteria.

Compliance

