11.1 Sample size

The primary outcome for both trials will be live birth rate (LBR) defined by the number of live births after 24 weeks gestation within the 15-month post-randomisation follow-up period relative to the number of women randomised.

Our review of the research literature including a Cochrane review of hysteroscopic removal of submucous fibroids and endometrial polyps (6) has found no reported estimates of the LBR in our proposed target populations. Although, two previously conducted RCTs included in the Cochrane review roughly indicate a doubling of pregnancy rates. The first quoted a clinical pregnancy rate (at 6-7 weeks) of approximately 214/1000 (21%) over 12 months in a sample of 42 women with fibroids (submucosal and mixed submucosal intramural) without surgery and a miscarriage rate (between 7 and 12 weeks) in those without surgery of approximately 556/1000 (56%) (35). Applying the miscarriage rate to the pregnancy rate (i.e. $0.21 * 0.56$) would give a LBR of approximately 10% over 12 months in the control arm (no resection). The second, in women with endometrial polyps undergoing IVF, detected an increase of pregnancy rates from 28% to 63%, with no miscarriage rate reported (36). We therefore estimate a usual care LBR of 10% within 15 months in the populations of women proposed for inclusion in this study, both for the submucous fibroid and endometrial polyp RCTs.

Assuming a 10% LBR in the no hysteroscopic removal (control) group and that an absolute increase of 10%, to a 20% LBR (a relative risk of 2.00) in the hysteroscopic removal (intervention) group is of clinical and practical importance. Then to have a 90% power of detecting this difference or more, in LBR rates between the groups, as statistically significant at the 5% two-sided level, will require 266 women per group (532 in total). Adjusting for a predicted attrition rate of 5% (due to potential difficulties of follow-up for patients who have been referred from other NHS Trusts) we will require 560 participants to be randomised.

A similar sample size will be required for RCT2 (polyp population) i.e. 560 participants, so a total of 1120 participants are required for RCT1 and RCT2 combined.

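### The per-protocol set is partly defined by the outcome: women who conceive while waiting for resection drop out of the intervention arm, while controls who conceive in the same months stay in

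*Protocol*

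**What the plan says.** Protocol section 11.2 analyses by intention to treat and then, under the analysis of secondary outcomes, adds: "We shall also repeat the above analyses on the per protocol population". At the least this covers the secondary binary outcomes listed just before it: 24-month live birth, clinical pregnancy, miscarriage, ectopic pregnancy, pre-term delivery, stillbirth and others. It can also be read as covering the primary outcome.

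The same section defines the set.

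- **Intervention arm:** the woman attends and receives the procedure, "following the sites usual procedures for hysteroscopic removal of submucous fibroids and / or endometrial polyps) within the first six-months post-randomisation".
- **Control arm:** the woman attends and is "not undergoing hysteroscopic removal of submucous fibroids or endometrial polyps procedure per protocol within the first six months post-randomisation".

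Section 6.1 foresees pregnancy before surgery. A woman allocated to resection who "has a positive pregnancy test before receiving hysteroscopic resection, the patient will remain in the trial and followed-up" stays under the usual schedule. Section 11.2 makes no matching provision for her in the per-protocol set.

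Three other passages bear on the size. Section 6.1 asks intervention women to use contraception before hysteroscopy where applicable, and has their other fertility treatment start after resection. Section 6.2 has controls start or resume treatment as soon as possible after randomisation. Section 7 lets some sites randomise during hysteroscopy, with no wait.

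**The concern.** To be resected, a woman must not be pregnant when surgery falls due. Requiring resection within six months therefore removes early conceptions from the intervention arm only. On the other side, a control removed for early resection is, by the same logic, a woman who had not yet conceived, so her removal raises the control rate. For live birth and clinical pregnancy both selections act against resection.

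For miscarriage, ectopic pregnancy, pre-term delivery and stillbirth the denominator is all women in the arm. Dropping pregnancies that begin before surgery can then lower the intervention rate and make resection look better.

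Early conceptions carry much of the 15-month result, because a birth by month 15 needs conception by about month 6, and the wait for surgery falls inside that window. Section 11.2 also warns that delayed or missed resection may leave only an estimate of the policy of allocating resection. Readers wanting the effect of surgery itself may therefore turn to the per-protocol table, and part of any contrast there would come from the definition of the set.

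**Working it through.** **The plan's own figures.** Section 11.1 starts from "Assuming a 10% LBR in the no hysteroscopic removal (control) group" and a target of 20%, with 90% power at 5% two-sided. For n per group:

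n = [1.96·√(2·0.15·0.85) + 1.2816·√(0.10·0.90 + 0.20·0.80)]² / 0.10² = 265.9, so 266.

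Then 2 × 266 = 532, and 532/0.95 = 560. The sample size reproduces and is not in question. It supplies the 10% control rate and the 10-point yardstick used below.

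**Assumptions the protocol does not supply.** Resection has no effect. Conceptions leading to live birth occur at a constant rate λ. Conception to birth takes 8.7 months, so conception must fall in the first 15 − 8.7 = 6.3 months. Surgery dates are independent of conception. From 1 − exp(−6.3λ) = 0.10, λ = 0.0167 per month.

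**Fixed wait w, no contraception.** Per-protocol intervention rate = 1 − exp(−λ(6.3 − w)). The control rate is 10.0% and the intention-to-treat difference is 0.

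| Wait | Per-protocol intervention rate | Difference (points) |
|---|---|---|
| 0 | 10.0% | 0 |
| 1 month | 8.5% | -1.5 |
| 2 months | 6.9% | -3.1 |
| 3 months | 5.4% | -4.6 |
| 18 weeks (4.1 months) | 3.6% | -6.4 |

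**24-month live birth, 3-month wait.** Control: 1 − exp(−15.3λ) = 22.6%. Per-protocol intervention: 1 − exp(−12.3λ) = 18.6%. Difference: -4.0 points.

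**Waits spread evenly over 1 to 5 months.** The mean of exp(−λW) is 0.951, so without contraception the per-protocol rate is 1 − 0.90/0.951 = 5.4%. For contraception users, who start trying only at surgery, the mean of exp(λW) is 1.052 and the rate is 1 − 0.90 × 1.052 = 5.4%. If a fraction c use contraception, the intervention rate by intention to treat is 10.0(1 − c) + 5.35c per cent.

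| Contraception use | Intention to treat, intervention | Per protocol, intervention | Selection (points) | Delay, also seen in intention to treat (points) |
|---|---|---|---|---|
| 0% | 10.0% | 5.4% | -4.6 | 0 |
| 50% | 7.7% | 5.4% | -2.3 | -2.3 |
| 90% | 5.8% | 5.4% | -0.5 | -4.2 |
| 100% | 5.4% | 5.4% | 0 | -4.6 |

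**Control crossover.** Suppose 10% of non-pregnant controls are resected by month 6. About 9.5% of the arm is then removed, with 0.5 percentage points of its births. The control per-protocol rate becomes (10.0 − 0.5)/(100 − 9.5) = 10.5%, which adds about 0.5 point to the gap.

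**Two possible repairs, no contraception, no effect.** Keep women who conceive before a planned date within six months: the set is then everyone with such a date, and the rate is 10.0%, unbiased apart from crossover. Keep every early conceiver regardless of planned date, with waits of 1 to 8 months: of all women, 5/7 have dates within six months and stay; of the remaining 2/7, only conceivers stay (3.2% of the arm, of whom 2.8 percentage points give birth in time). The rate is (7.1 + 2.8)/(71.4 + 3.2), about 13.4% on unrounded figures, against 10.5% in controls: a false benefit of about 3 points.

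**The case against.** The strongest reply is that large figures need women not to use contraception, whereas section 6.1 asks them to where applicable and starts their other fertility treatment only after resection. Both reduce conception before surgery. Section 8.1 targets resection of everyone before 3 months (green at 80%), and women randomised during hysteroscopy have no wait. This stands as a limit on size. It does not remove the asymmetry: the request is conditional, uptake is not stated, section 6.1 itself plans for pregnancies before surgery, and it also allows an 18-week pathway and pandemic delay.

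A reader might infer that the per-protocol analysis will show about 5 points of harm whenever resection does nothing. The documents do not support that. It is one scenario, with no contraception and waits of 1 to 5 months. With high contraception use a similar gap appears, but nearly all of it is delay, which intention to treat shows too. Nor does every outcome lean against resection. A woman who miscarries and is then resected within six months also stays in the set, so the exclusion is not total.

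The set is only supportive. The primary outcome has its own adjustment for non-compliance and contamination, and section 11.2 plans rank-preserving and inverse-probability methods for informative departures in the time-to-event analyses. That limits the seriousness of the point. The secondary binary outcomes, however, are given no such adjustment beyond the per-protocol repeat.

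**Conclusion.** The point holds as a fault in a stated definition. Per-protocol membership depends on early conception in one arm and not in the other. For live birth and clinical pregnancy the selection is against resection; for adverse pregnancy outcomes it can run the other way.

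With no effect, a 10% live birth rate and waits of 1 to 5 months, intervention-arm selection runs from about -4.6 points with no contraception to nil with universal use, against a target difference of 10. Control crossover of 10% adds about 0.5 point. These sizes rest on assumed waits, contraception uptake, a constant conception rate and a fixed interval to birth; only the 10% rate and the 10-point target come from the protocol. A reader might also infer that the trial's main conclusion is at risk. It is not: the intention-to-treat analysis does not use this set, and the sample size is sound.

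**What to change.** **Preferred.** In section 11.2, for pregnancy and birth outcomes, replace the per-protocol repeat with the non-compliance and contamination adjustment already specified for the primary outcome, extended to the secondary binary outcomes. It works from the randomised groups and does not select women by whether they were still not pregnant at surgery. Cost: a little more analysis work.

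**If a per-protocol set is kept.** Retain intervention women who conceive before a planned resection date that falls within six months of randomisation. Do not retain all early conceivers, which creates the opposite bias when some waits exceed six months. State that selection through control crossover remains and that delay is not removed. Cost: the planned resection date must be available for the women concerned. Table 2 lists details of hysteroscopy received, and section 6.1 records attendance and receipt, so it should be checked whether the planned date is captured.

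Both options change the analysis only and leave clinical care as it is.
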